### 9.2.2.1.2. Initial Treatment Visit (Month 0) and Every 4 Months Including End of Study Visit

**Pre-injection assessments** will be performed prior to administration of each dose of TEGSEDI at study visits. Pre-injection assessments will include:

- Abbreviated Physical examination, i.e. weight and vital signs, general appearance, dermatological, respiratory, cardiovascular and abdomen. (except Month 0 if they were performed at Screening)
- Concomitant Medications
- Laboratory testing
  - IgE, IgG, IgM (see [Annex 1](#))
  - Inflammatory markers: C-reactive protein (CRP), Erythrocyte sedimentation rate (ESR), interferon  $\alpha$  (IFN-  $\alpha$ ), IFN- $\beta$ , Chemokines (Macrophage inflammatory protein (MIP)-1a and membrane cofactor protein (MCP)-1), Granulocyte-macrophage colony stimulating factor (GM-CSF), interleukin (IL)-1 $\alpha$ , IL-1 $\beta$ , IL-6, IL-8, IL-12. Tumor necrosis factor –  $\alpha$  (TNF-  $\alpha$ ) (see [Annex 1](#))
  - ADA sampling at Month 0 visit pre-injection first dose and at End of Study visit, pre-injection
  - Urine pregnancy testing for women of childbearing potential
  - Additional blood samples will be drawn and stored for possible future non-genetic testing in this study.
- Adverse events since last study visit

**Post injection assessments** will be made at 1 hour  $\pm$  15 minutes; 2 hour  $\pm$  15 minutes; 4 hour  $\pm$  30 minutes; 8 hour  $\pm$  30 minutes and 20-30 hours following injection of TEGSEDI. Post-injection assessments will include:

- Vital signs
- Laboratory testing
  - IgE, IgG, IgM (see [Annex 1](#))
  - Inflammatory markers: CRP, ESR, IFN- $\alpha$ , IFN- $\beta$ , Chemokines (MIP-1a and MCP-1), GM-CSF, IL-1 $\alpha$ , IL-1 $\beta$ , IL-6, IL-8, IL-12, TNF-  $\alpha$  (see [Annex 1](#))
  - Additional blood samples will be drawn and stored for possible future non-genetic testing in this study
- Adverse events post injection at study visit
- The ADA sample is only drawn post injection, at the 20-30 hour time point, in the event of a hypersensitivity reaction

In addition to these study visits, the patient will be monitored according to the applicable product label.

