### 8.2.2.2 Adverse Events Occurring Within 24 hours of TEGSEDI Administration

AEs occurring within 24 hours of administration of TEGSEDI are defined as all AEs with an onset date/time no longer than the 24-hour planned timepoint using a window interval from 20 to 30 hours after the date/time of the injection. For AEs with missing time of onset, AEs occurring within 24 hours of TEGSEDI administration are defined as AEs with an onset date of the same day as the TEGSEDI administration or the subsequent day. This rule will also be applied for missing time of administration of TEGSEDI.

The incidence of AEs occurring within 24 hours post TEGSEDI administration will be summarized at each visit and overall using counts and percentages in the evaluable set. The incidence will be reported with 95% confidence intervals (CIs). Additionally, a summary of AEs occurring within 24 hours post TEGSEDI administration will be displayed by SOC and PT and will be summarized at each visit and overall.

The denominator for the calculation of the percentages by visit will be the number of patients who received a TEGSEDI administration for the specific visit. The denominator for the calculation of the percentages for the overall occurrence of AEs in any visit will be the number of patients in the evaluable set. These denominators will also be presented in the table.

The time from the injection of TEGSEDI until the occurrence of the first AE will be summarized by each visit and overall using descriptive statistics for continuous variables. The time (hours) will be calculated as:

(Onset date/time of the AE – injection date/time of TEGSEDI)/3600

Time from injection of TEGSEDI until the onset of the AE will only be summarized for the AEs with available time for the onset of the AE and available time of TEGSEDI injection. Where time is not available, the AE will be included in the incidence count but will not be included in the summary of time to onset.

The duration of AEs occurring within 24 hours of TEGSEDI administration (in hours) will be calculated as:

- $(\text{Date/time of resolution} - \text{date/time of onset})/3600$

Duration of the AEs will only be calculated for AEs with an outcome of "Recovered" or "Recovered with sequelae" for which date/time for onset and resolution is available.

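### The calendar-day rule for AEs without a time has no exclusion for an onset known to precede the injection or to follow the 30-hour limit

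*Combined protocol and SAP*

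**What the plan says.** SAP 8.2.2.2 sets two rules for deciding whether an AE belongs to an injection.

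- **Both times known.** Onset must be "no longer than the 24-hour planned timepoint using a window interval from 20 to 30 hours after the date/time of the injection". At its widest this is 30 hours.
- **Onset time missing.** The AE qualifies by date alone: "AEs with an onset date of the same day as the TEGSEDI administration or the subsequent day". The next sentence extends this to the injection: "This rule will also be applied for missing time of administration of TEGSEDI".

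The section then treats untimed AEs differently by summary. For time to onset, "the AE will be included in the incidence count but will not be included in the summary of time to onset"; that summary "will only be summarized for the AEs with available time for the onset of the AE and available time of TEGSEDI injection". Duration is likewise limited to resolved AEs "for which date/time for onset and resolution is available".

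On collection, protocol v2.0 section 9.2.2.1.2 lists "Adverse events since last study visit" among the pre-injection assessments and "Adverse events post injection at study visit" among those at 1, 2, 4, 8 and 20-30 hours. SAP Tables 1 and 2 carry only the post-injection AE row. The SAP's Introduction cites protocol version 3.0, whereas the protocol supplied is v2.0.

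**The concern.** The date rule has no exception for an AE whose onset is untimed but whose order relative to the injection is known. A headache mentioned at the pre-injection check, entered with that day's date and no clock time, becomes a post-injection AE. At the other end, an untimed AE dated the next day qualifies up to midnight, although a timed AE with the same onset could be too late. Timed and untimed AEs are thus judged against different windows at both ends.

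The 24-hour flag drives the study's central results:

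- incidence by visit and overall, with confidence intervals, and the SOC/PT tables (8.2.2.2);
- the comparison of injections with and without preventive measures;
- the exploration of risk factors;
- vital signs and cytokines by presence or absence of a 24-hour AE (8.2.3, 8.2.4).

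An AE that began before an injection cannot have been caused by it, yet it would put the patient in the AE-present group for that visit.

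The time course of onset is also named in the objective, and no visible onset summary retains untimed AEs.

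**Working it through.** **The plan's own figure.** The protocol's Study Size section gives 95% probability of detecting an AE of 4% frequency in 75 patients: 1 − 0.96^75 = 0.953. This reproduces, and the present point does not affect it.

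**Does another rule remove the misplaced AEs?** The TEAE definition in SAP 8.2.1.1's counterpart for AEs, section 8.2.2.1, is anchored to the first on-study dose. At any visit after Month 0, an AE that began that morning before the injection is already treatment-emergent. The definition also has no rule for missing times. No visible text specifies a sensitivity analysis for date-placed AEs.

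**Width of the date rule.** Day of injection plus next day = 48 h. Injection times are not in the documents, so I assume a range. With injection at hour *h* of the day (for *h* up to 18):

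- hours before injection = *h*
- end of window after injection = 48 − *h*
- hours past the 30 h limit = 48 − *h* − 30 = 18 − *h*

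| Injection | Before injection | Window ends | Past 30 h |
|---|---|---|---|
| 08:00 | 8 h (17% of 48) | 40 h | 10 h |
| 09:00 | 9 h (19%) | 39 h | 9 h |
| 12:00 | 12 h (25%) | 36 h | 6 h |
| 16:00 | 16 h (33%) | 32 h | 2 h |

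In each row 30 of the 48 h (62.5%) coincide with the 0-30 h window. The percentages are shares of clock time. They would be shares of untimed AEs only if those fell evenly over the two days.

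**What one misplaced AE can do.** With 75 evaluable patients (assumed equal to the planned minimum), a patient counted only because of a misplaced AE adds 1/75 = 1.33 points to overall incidence. For example, 3/75 = 4.0% (Clopper-Pearson 95% CI 0.8 to 11.2) becomes 4/75 = 5.3% (1.5 to 13.1). A patient with another qualifying AE is unaffected.

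**Onset summary, direction only.** Patients are assessed up to 8 h (8.5 h with the window) and next at 20-30 h. Assume one AE per injection, onset uniform over 0-24 h, and times missing only for onsets between 8.5 and 20 h. If half of those are timed, the effective weight is 8.5 + 0.5 × 11.5 + 4 = 18.25. The median is then 8.5 + (9.125 − 8.5)/0.5 = 9.75 h, against 12.0 h with all timed. The share with onset by 8.5 h is 8.5/18.25 = 47%, against 8.5/24 = 35%. If missing times are unrelated to place, nothing shifts.

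**The case against.** The strongest reply is that the rule is prespecified and cautious: when a time is missing, a safety study should count the AE rather than lose it. Hours cannot be computed without times. Descriptive statistics include n, a listing of all AEs is planned, and no hypothesis is tested. This stands as a reason to keep the date rule as the default. It does not justify counting an AE whose onset is known to lie outside the window.

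A reader might infer that the onset summary is in fact biased towards AEs seen in clinic. The documents do not support that. Nothing says which AEs will lack a time, and onset can be asked at the return visit. The planned statistic is also time to the first AE, so losing a later AE changes nothing for a patient with an earlier timed one. If an untimed first AE is followed by a timed one, the shift could even go the other way.

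A reader might also infer that nearly all untimed AEs could be placed from data already collected. That is not shown either. The SAP schedules omit the row for AEs since the last visit, protocol version 3.0 was not supplied, and no visible eCRF item records the assessment at which an AE was first noted. The mock tables are not shown, so a safeguard there cannot be ruled out.

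**Conclusion.** The point holds as a defect in a stated rule. SAP 8.2.2.2 keeps in the 24-hour set an untimed AE known to have begun before that visit's injection or after 30 hours, and no other visible text removes it. The mismatch between the timed and untimed windows is 18 of 48 hours for any injection between 08:00 and 16:00: 8 + 10 at the early end of that range, 16 + 2 at the late end.

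The effect on incidence cannot be sized, because the number of untimed AEs is unknown. The 17% to 33% of the window that precedes dosing must not be read as inflation of incidence. It is not even a share of untimed AEs without the even-spread assumption, which is incompatible with the assumption in the onset example that untimed AEs arise only at home after the 8-hour check.

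The loss of untimed AEs from time to onset is certain from the text. A tilt towards early onsets is a plausible consequence, not a demonstrated one.

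**What to change.** In SAP 8.2.2.2:

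1. Keep the calendar-day rule as the default, but exclude an untimed AE when available information shows onset before the injection or after the 30-hour limit. Examples are a pre-injection record, a record at an earlier assessment, or absence at the 20-30 hour visit. Absence shows only that onset followed that visit; after a visit at 20 h, up to 10 h of the window remain. The SAP should therefore say whether the limit is the actual visit or 30 h.
2. Add a categorical onset table (0-1, 1-2, 2-4, 4-8, 8 h to return visit, unknown) covering all 24-hour AEs. Place untimed AEs by the assessment at which they were first recorded where the eCRF identifies it, and otherwise as unknown. Keep the hour-based summary for timed AEs.
3. Report the number of untimed AEs, and show incidence with and without AEs placed by date alone.

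The cost is SAP wording, slightly more programming and one extra table. Whether more is needed depends on the eCRF: where it does not hold the assessment, some AEs stay in the unknown row. That is a limitation, but a visible one.

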## 8 Statistical Methods

For this phase IV study, only descriptive analyses will be provided. No hypothesis testing will be done. However, 95% confidence intervals will be provided where indicated using the Clopper-Pearson method. Descriptive statistics will comprise the number of observations (n), mean, standard deviation (SD), standard error (SE) of mean, median, minimum, and maximum for continuous variables, and n and percent for categorical variables.

The overall study baseline is defined as the last available observation prior to the first on study TEGSEDI administration.

For each study visit on treatment, changes in vital signs and cytokines/inflammatory markers post-injection of TEGSEDI are calculated relative to the pre-injection values, not relative to the overall baseline values. For visit level summarization, analyses will be performed by the study visit using data as collected in the electronic case report form (eCRF).

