### 8.1 Analysis Populations

The safety set includes all patients who received at least one dose of TEGSEDI while enrolled in this study protocol. The safety set will be used in the summary of demographics, medical history, patient disposition, AEs, concomitant medications and ADA (Anti-drug antibody).

The evaluable set includes patients in the safety set having at least one post-dose assessment. The evaluable set will be used in the summaries of AEs by study visit and vital signs and cytokines/inflammatory markers recorded over a 24-hour period.

Listings will be run on the safety set.

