### Preventive Measures Used Prior to the TEGSEDI Injection

The incidence of AEs occurring within 24 hours will also be calculated for injections with preventive measures as reported by the eCRF question "Did the patient take any preventive measures prior to the administration of the dose". The incidence of AEs will be calculated for TEGSEDI administrations with and without preventive measures by visit and overall for any visit. The denominator for the calculation of the percentages by visit will be the number of patients who received a TEGSEDI administration with or without preventive measures, respectively. For the calculation of the overall occurrence of AEs with or without preventive measures, the patients will be included in the denominator if the patient received at least one TEGSEDI administration with or without preventive measures, respectively.

The preventive measures as reported on the Dosing at Visit eCRF will be provided as listings.

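### The by-visit 24-hour AE incidence is divided by patients dosed, with no display of how many were assessed, so incomplete follow-up can lower it unseen

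*Combined protocol and SAP*

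**What the plan says.** SAP 8.2.2.2 is the analysis of the study's own endpoint, AEs within 24 hours of an injection given at a study visit. The incidence "will be summarized at each visit and overall using counts and percentages in the evaluable set", with 95% confidence intervals. SAP 8 names the interval: "95% confidence intervals will be provided where indicated using the Clopper-Pearson method".

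There are two denominators. By visit it is "the number of patients who received a TEGSEDI administration for the specific visit". For any visit, the denominator for "the overall occurrence of AEs in any visit will be the number of patients in the evaluable set". The SAP adds that "These denominators will also be presented in the table".

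SAP 8.1 defines the set at patient level: "The evaluable set includes patients in the safety set having at least one post-dose assessment". The assessment need not be at the visit being summarised, and it need not be an AE assessment.

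The preventive-measures part of 8.2.2.2 follows the same pattern. Its by-visit denominator is "the number of patients who received a TEGSEDI administration with or without preventive measures, respectively".

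On missing data, 8.2.2.2 has rules for a missing AE onset time and a missing injection time. It has none for a patient who was injected but not assessed afterwards.

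**The concern.** The endpoint depends on observation over a fixed window. Protocol 9.1.2 schedules contacts at 1, 2, 4 and 8 hours and a separate return to the clinic at 20-30 hours. The counting window in SAP 8.2.2.2 runs to that last contact. A patient who goes home after the 8-hour check and does not come back has been observed for only part of the window, yet enters the denominator in full. A patient assessed at Month 0, and later injected at Month 8 without follow-up, does the same at Month 8.

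If nothing is recorded for these patients, they are indistinguishable from patients who were watched throughout and had no AE. Three readings of the tables are then at risk:

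- the level of the incidence, which can only be pulled down;
- the pattern across visits, if next-day returns become less complete over time;
- the contrast between injections with and without preventive measures, if follow-up differs between them.

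The interval is affected too, because its n includes people who were not fully observed.

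**Working it through.** **The plan's own figure.** The documents give no expected by-visit incidence. The related figure is in protocol 9.4: 75 patients give 95% probability of detecting an AE that occurs in 4% of patients. This reproduces: 1 − 0.96^75 = 0.953. The calculation takes all 75 as observed.

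**Inputs.**
- Denominator: patients dosed at the visit (SAP 8.2.2.2).
- Interval: 95% Clopper-Pearson (SAP 8).
- True incidence p = 15%: assumed for illustration.
- Share m of dosed patients whose post-dose follow-up is missing or incomplete: not in the documents; 10% and 20% assumed.
- Share c of those patients' AEs that still reach the database, through the checks up to 8 hours or later reporting: not in the documents; 0, one half and 1 assumed.

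**Reported incidence on the dosed denominator.** Fully assessed patients contribute p(1 − m) and the others pmc, so reported = p[1 − m(1 − c)].

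| m | c = 0 | c = 0.5 | c = 1 |
|---|---|---|---|
| 10% | 0.15 × 0.90 = 13.5% | 0.15 × 0.95 = 14.3% | 15% |
| 20% | 0.15 × 0.80 = 12.0% | 0.15 × 0.90 = 13.5% | 15% |

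The error is never upward, and it vanishes when every such AE is captured.

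**Effect on the interval.** Take 75 dosed, 15 patients with an AE, and no AE captured in unassessed patients (c = 0):

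| n used | Incidence | 95% CI |
|---|---|---|
| 75 dosed | 20.0% | 11.7-30.8 |
| 67 assessed | 22.4% | 13.1-34.2 |
| 60 assessed | 25.0% | 14.7-37.9 |

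**Choice of sensitivity analysis.** Two candidates, under the same assumptions with c = 0.5:

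1. Keep patients with the 20-30 hour assessment, plus anyone with an AE already recorded. The denominator is (1 − m) + pmc and the numerator p(1 − m) + pmc. At m = 10% this gives 0.1425/0.9075 = 15.7%; at m = 20%, 0.135/0.815 = 16.6%. It exceeds the true 15% because it retains the early AE cases and drops the AE-free patients who missed the return.
2. Restrict numerator and denominator alike to patients with the 20-30 hour assessment. This gives p(1 − m)/(1 − m) = p = 15%, provided that missing the return is unrelated to having an AE.

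The second is the better choice.

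**The case against.** **AEs do not have to be found at a timed assessment.** A reader might infer that every injected but unassessed patient is counted as AE-free. The documents do not support that. SAP 8.2.2.2 places an AE in the window by its recorded onset, and an AE with no onset time still counts if dated the injection day or the day after. Protocol 11.4.2 has the investigator record AEs that are observed or volunteered. Protocol 9.2.2.1.2 asks, before each injection, about AEs since the previous visit. A patient with no post-dose assessment at any visit is outside the evaluable set altogether. All of this stands, and it is why the point is limited to patients with no AE otherwise recorded.

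**How far late reporting is retained is unclear.** The schedules in SAP section 6 lack the row for AEs since the previous visit that protocol v2.0 carries. It is tempting to conclude that late-reported AEs are lost. That does not follow: the SAP was written for protocol v3.0, which is not among the documents, and SAP 8.2.2.1 still summarises AEs over the whole treatment period and lists all of them.

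**The worst case is unlikely.** The dose is given in clinic with checks to 8 hours, so a dosed patient with no AE assessment at all should be uncommon. The likelier gap is a missed next-day return, with earlier AEs already captured. At 10% missing and half captured, 15% becomes 14.3%, which is small beside the intervals above. This is fair, but the tables as planned would not show which case applies.

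**Patients dosed is a usual safety denominator, the analysis is descriptive, and the denominators are shown.** The first two are good reasons to keep it as primary. The third helps only partly: the number shown by visit is the number dosed, not the number observed.

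**Conclusion.** The point holds in limited form. The by-visit rule, combined with a patient-level evaluable set, counts a dosed but incompletely observed patient as a non-event unless an AE is otherwise recorded. Any resulting bias in the 24-hour incidence is downward. The same applies to the preventive-measures tables and, at patient level, to the any-visit incidence.

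The size cannot be found from the documents. At an assumed true incidence of 15% with 10% to 20% missing, the reported figure is 13.5% to 14.3% if half of the AEs are captured in the 20% and 10% cases respectively, 12.0% to 13.5% if none are, and unbiased if all are.

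Two stronger conclusions are not supported. The dosed denominator need not be replaced, since it is a defensible convention and the fault is the missing visit-level information. Nor can an artificial decline over visits be predicted: it would need returns to become less complete with time, and the documents say nothing on that.

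**What to change.** In SAP 8.2.2.2, including the preventive-measures part:

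1. Keep patients dosed at the visit as the primary denominator, and state that dosed patients without a recorded AE count as non-events whether or not they were assessed.
2. In each by-visit and preventive-measures table, show beside the number dosed the number with any post-dose AE assessment and the number with the 20-30 hour assessment at that visit.
3. Add a sensitivity incidence with Clopper-Pearson interval in which both numerator and denominator are restricted to patients with the 20-30 hour assessment at that visit. Do not add back patients solely because an AE was already recorded, for the reason shown in the working.

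No new data are needed, because the assessments are already scheduled. The cost is SAP wording, the added counts, one extra row per table and a smaller n in that row. The sensitivity row also assumes that missing the return is unrelated to having an AE. If patients with an AE are more or less likely to come back, it is biased too, so it should be read beside the primary figure and not in place of it.

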## **Data Analysis**

Incidence (95% confidence interval), onset, and duration of each AE occurring within 1 day of TEGSEDI administration will be summarized by visit and overall in any visits. The rates of AEs

occurring after preventive measures will also be summarized. Resolution time with and without treatment administered for these AEs will be summarized.

For each study visit while on treatment, the results and changes from pre dose baseline in vital signs and cytokines and inflammatory markers will be summarized using descriptive statistics for patients with and without AEs within 1 day of TEGSEDI administration.

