### **9.6.4. Safety Analysis**

Patient incidence rates of all AEs will be tabulated by Medical Dictionary for Regulatory Activities (MedDRA) system organ class (SOC), and by MedDRA preferred term (PT). Narratives of deaths, all discontinuations, serious AEs, pregnancies and AEs of special interest (AESI) will also be provided.

All treatment emergent AEs, all treatment emergent AEs potentially related to TEGSEDI, all treatment emergent serious AEs, and all treatment emergent serious AEs potentially related to TEGSEDI will be summarized.

Incidence (95% confidence interval) of AEs occurring within 1 day of TEGSEDI administration, and time to onset from TEGSEDI injection and duration of these AEs will be summarized by visit and overall in any visit. The rates of AEs during the 1-day visit occurring after preventive measures will also be summarized. Resolution time with and without treatment administered for the AEs will be summarized.

For each study visit on treatment, the result and change from pre-dose baseline in vital signs (body temperature, heart rate, respiratory rate, and systolic, diastolic blood pressure) and cytokines/inflammatory markers will be summarized using descriptive statistics for all patients in the Evaluable Set and by presence/absence of AEs within 1 day of TEGSEDI administration.

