### 3 Study Objectives

The objective of the study is to characterize adverse events (AEs) occurring within 24 hours of TEGSEDI administration in adult patients with hATTR-PN and in individual patients with respect to time course of AE onset, vital sign changes, preventive measures, treatment required, risk factors, and subsequent adverse outcomes.

The endpoints of the study are AEs occurring within the first 24 hours of TEGSEDI administration at study visits, changes in vital signs and cytokines and inflammatory markers 24-hour post-injection with additional assessments of:

- Preventive measures used prior to the injection
- Treatment of AEs post 24 hour injection of TEVESDI at study visits
- Identification of risk factors for AEs occurring within the first 24 hours of TEVESDI administration at study visits
- Correlation of subsequent adverse outcomes

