## 8.2.2 Adverse Events

### 8.2.2.1 Treatment-emergent Adverse Events (TEAEs)

TEAEs are defined as AEs with an onset date/time on or after the date/time of the first on study administration of TEGSEDI. Related TEAEs are TEAEs with a reported relationship of "Possible" or "Related". TEAEs with a missing relationship will also be counted as Related. Serious Adverse Events (SAEs) will be indicated as such in the eCRF and can be defined as treatment emergent, based on when the SAE initiated. AEs will be summarized using the safety set for the treatment period among both patients who develop a hypersensitivity reaction and those patients who do not develop a hypersensitivity reaction.

TEAEs will be summarized as follows:

- Overview of Treatment-emergent AEs
- Treatment-emergent AEs by System Organ Class and Preferred Term
- Treatment-emergent AEs by System Organ Class, Preferred Term and Severity
- Treatment-emergent AEs Related to TEGSEDI by System Organ Class and Preferred Term
- Treatment-emergent AEs Related to TEGSEDI by System Organ Class, Preferred Term and Severity
- Treatment-emergent Adverse Events of Special Interest (AESI) by System Organ Class and Preferred Term

 	
Title: Statistical Analysis Plan
 
Program Name: "A Phase 4 Safety Study Assessing the Adverse Events Occurring Within 24 Hours of TEGSEDI Administration in Patients with polyneuropathy of Hereditary Transthyretin-mediated Amyloidosis (hATTR-PN)"
 
Protocol #: TEG4004
 
[REDACTED]
 
Version: Final 2.0 Effective Date: 06 October 2023

--	---

- Treatment-emergent AESIs by System Organ Class, Preferred Term and Severity
- Treatment-emergent Serious AEs by System Organ Class and Preferred Term
- Treatment-emergent Serious AEs Related to TEGSEDI by System Organ Class and Preferred Term
- Treatment-emergent AEs leading to discontinuation of TEGSEDI by System Organ Class and Preferred Term

AEs will also be presented in data listings as follows:

- Listing of All Adverse Events
- Listing of Adverse Events Leading to Discontinuation
- Listing of Serious Adverse Events
- Listing of Adverse Events of Special Interest

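### The SAP's only onset summary is time to the first AE after injection, with no stated breakdown by AE type, so later onsets in patients with several AEs are left out of it

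*Combined protocol and SAP*

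**What the plan says.** SAP 8.2.2.2 sets out the onset analysis in one sentence: "The time from the injection of TEGSEDI until the occurrence of the first AE will be summarized by each visit and overall". The summary uses descriptive statistics for continuous variables. A rule on missing clock times follows: time to onset "will only be summarized for the AEs with available time for the onset of the AE and available time of TEGSEDI injection". AEs without a time stay in the incidence count.

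Two other analyses in the same section have a wider scope. For incidence, "a summary of AEs occurring within 24 hours post TEGSEDI administration will be displayed by SOC and PT". For duration, "The duration of AEs occurring within 24 hours of TEGSEDI administration (in hours) will be calculated as" resolution minus onset, so it applies to AEs in the window generally and not only to the first.

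The supplied protocol, v2.0, describes onset more broadly. Its abstract (Data Analysis) plans that "onset, and duration of each AE occurring within 1 day of TEGSEDI administration will be summarized by visit and overall in any visits". Section 9.6.4 plans that "time to onset from TEGSEDI injection and duration of these AEs will be summarized by visit and overall in any visit", where the AEs meant are those within one day of injection. The SAP's own objective (section 3) is to characterise AEs "in individual patients with respect to time course of AE onset, vital sign changes, preventive measures, treatment required, risk factors".

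**The concern.** How AE onset is spread over the day after injection is the first attribute named in the objective, and patients are assessed at 1, 2, 4, 8 and 20-30 hours after injection. Time to the first AE answers a narrower question: how soon something of any kind happens. If a patient has a minor local AE early and another AE hours later, only the early time enters the summary.

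At stake is whether the report will contain a summary of when particular kinds of AE begin. Hypersensitivity reactions are the clearest case, because the study gives them their own schedule, ADA sampling and follow-up. As written, the SAP text provides no onset summary for them.

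**Working it through.** **1. Figures in the plan.** The documents give no figure on onset. The only design figure is the 95% chance of seeing an AE of 4% frequency in 75 patients (protocol 9.4). It reproduces, 1 − 0.96^75 = 0.953, and plays no part in this point.

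**2. The texts side by side.**

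| Place | AEs covered by onset | Split by AE type stated for onset? |
|---|---|---|
| Protocol v2.0, abstract, Data Analysis | each AE within 1 day | not stated |
| Protocol v2.0, 9.6.4 | all AEs within 1 day | not stated |
| SAP 8.2.2.2 | the first AE | no |

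The SOC and PT display in SAP 8.2.2.2 belongs to the incidence paragraph. Hypersensitivity is counted by visit (SAP 8.2.5) and summarised by ADA status (8.2.8), and neither place mentions time of onset. No other SAP section summarises onset.

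**3. Direction.** The first onset after an injection is the minimum of that patient's onsets after it. Any onset left out is therefore the same or later, never earlier.

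**4. Small example (all counts assumed).** At one visit, 20 patients have a local AE at 0.25 h and 10 have a systemic AE at 6 h; 7 patients have both.
- Values in the summary: 20 + (10 − 7) = 23.
- The median is the 12th ordered value. The first 20 are 0.25 h, so the median is 0.25 h.
- Systemic onsets kept: 3 of 10 (30%). Left out: 7 of 10 (70%).
- With an overlap of 0, 5 or 10 patients, the share left out is 0%, 50% or 100%.

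**5. Range by simulation (all inputs assumed; 1,000,000 injections per scenario).** A minor AE follows 10%, 25% or 50% of injections, with exponential onset and mean 1 h. A later reaction follows 4%, 10% or 20%, with lognormal onset, median 6 h and log-SD 0.6. The two are independent, and onsets beyond 24 h are dropped.

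| Minor AE rate | Reaction onsets left out | Median time to first AE at reaction rate 4% / 10% / 20% |
|---|---|---|
| 10% | 9.8-9.9% | 1.13 / 2.28 / 3.83 h |
| 25% | 24.2-24.7% | 0.82 / 1.04 / 1.56 h |
| 50% | 48.8-49.0% | 0.73 / 0.80 / 0.91 h |

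The median onset of the reactions themselves is 5.94 to 5.99 h throughout. The share left out is close to the share of injections with an earlier minor AE. Summarising every timed AE by type would keep all of these onsets.

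**The case against.** The strongest reply is that the SAP is ambiguous rather than restrictive. After the sentence on the first AE, the text speaks of AEs in the plural, which would fit onset computed per AE or per first occurrence of each term. The mock tables in Appendix B are not in the supplied text and might show a breakdown. Both points limit certainty. But the plural wording is a rule for missing times and does not clearly restore a per-AE summary, and the SAP text should state the analysis whatever the table shells show.

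A reader might infer more than the documents support:
- *That the SAP departs from its governing protocol.* The SAP implements version 3.0 of 23 May 2023; the supplied protocol is v2.0. The wording of version 3.0 cannot be checked. The mismatch with the SAP's own objective does not depend on it.
- *That onset alone is collapsed over AE types.* Duration has no SOC or PT split either; it is split only by whether treatment was given. The difference between the two is first AE against all AEs.
- *That the study exists to time later reactions and that the summary is biased.* The objective covers all AEs within 24 hours. Time to first AE is a valid but narrower quantity, and the analysis is descriptive with no hypothesis testing.
- *That later onsets are lost.* SAP 8.2.2.1 plans a "Listing of All Adverse Events" as well as SAE and AESI listings, and protocol v2.0, 9.6.4, plans narratives for SAEs and AESIs among others. The columns of the listings are not described, and a listing is not the summary that the protocol text plans.

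Protocol 11.4 also asks investigators to group signs and symptoms under one diagnosis where possible. That reduces multiple records of one reaction but does not merge unrelated local and systemic AEs.

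**Conclusion.** The point holds as a mismatch of scope: the onset rule stated in the SAP covers less than its own objective and less than the supplied protocol text. Whenever a patient has more than one AE after an injection, later onsets drop out of the onset summary, though not out of the data.

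The size cannot be fixed from the documents. On the assumptions shown, about 10% to 49% of later-reaction onsets would be omitted, with a median time to first AE of 0.7 to 3.8 h against about 6 h for the reactions. These figures illustrate the mechanism and do not predict this study's results; with no overlap the omission is nil. The conclusion rests on reading the first AE literally and on there being no breakdown in the unsupplied mock tables. It should be corrected, but it does not threaten the study's conduct or its incidence results.

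**What to change.** Replace the onset sentence in SAP 8.2.2.2 with:

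*Time from injection to onset will be summarised for all AEs within 24 hours (first occurrence of each PT per patient and visit), by visit and overall, with a breakdown by SOC and PT pooled over visits and separately for hypersensitivity reactions; time to the first AE of any type will also be shown.*

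This also settles how repeated AEs are counted. Align the mock tables with it, and check the wording against protocol version 3.0.

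The cost is one sentence and one extra table from onset times already collected. With about 75 patients some PT rows will be sparse, even pooled over visits; individual values can be listed for those.
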